3.1 Study design

The CABGpreHAB feasibility study is designed as a randomized pilot study, aiming to assess the feasibility of a multimodal prehabilitation intervention plus usual care versus usual care alone in patients awaiting elective CABG surgery. It is an investigator-initiated study designed as an open-label, single-center randomized controlled feasibility study (allocation ratio 1:1) with blinded outcome assessment, designed to assess the method proposed for use in a larger RCT. This protocol follows guidance from Standard Protocol Items: Recommendations for Interventional Trials (SPIRIT).⁶⁰ The CABGpreHAB study will be registered at www.ClinicalTrials.gov before initiation.

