3.6 Sample size and power

As the primary aim of this study is to evaluate feasibility, there is no formal requirement for a formal power calculation.⁶² Sample sizes between 24 and 50 have been recommended.^{63,64} A sample size of 25 patients in each group was chosen as it seems reasonable to provide outcome data in a small sample, and at the same time a sample size large enough to investigate the additional aspects that are being assessed for feasibility⁶⁵ informing a future power calculation for a full-scale RCT.

4. Selection and allocation of participants

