7.1 Primary outcome

Feasibility outcomes include:

Recruitment and retention rates. The recruitment rate will be determined by the number of individuals who participate in the study out of those who are eligible/admissible but refused to participate. First, we will evaluate the number of patients we are able to include in the study during the inclusion period. A proportion of 60% or more of patients awaiting elective CABG surgery who are eligible for the study is acceptable. Retention will be assessed by the percentage of participants who remain in the study from beginning to end of study (30 days post-surgery).

Attrition rates. Attrition is defined by the number of individuals who give consent to participate in the study but drop out before the end of the intervention period, regardless of group allocation.

Fidelity. Fidelity of delivery of the webcam-based exercise training intervention will be assessed qualitatively by 8-10 semi-structured interviews the day before surgery by a research nurse.

Adherence rates. Adherence to the interventions will be measured by using the number of telephone counselling and tele-exercise sessions delivered out of the theoretical number that could have been delivered based on the surgical wait time of each participant. Adherence to the homebased tele-exercise training sessions and telephone counselling by evaluating the number of sessions applied in the intervention group. This will be collected by patient recorded physical activity logbook, by weekly phone calls and completed by accelerometer data. Adherence with the prehabilitation program will be assessed against the target of individuals achieving > 70% of the prescribed exercise program (self-reported) + during the study follow-up with phone calls. Inclusion in the CABGpreHAB study must be attractive to at least 30% of eligible patients who meets the inclusion criteria. The interventions must be widely accepted, with at least 70% of included participants completing 70% or more of the planned sessions in the intervention group. This will be assessed by interviews addressing reasons for withdrawals from the study and at which stage of the study these occur.

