Safety: Safety of the intervention will be determined based on the number and nature of adverse events (AE), which is defined as any discomfort or symptoms of angina pectoris that will prevent a patient to take part in the physical tele exercise sessions or symptoms that require medical attention. Adverse event (AE), serious AE (SAE), serious adverse reaction (SAR), and suspected unexpected serious adverse reaction (SUSAR) will be monitored during the trial counting the number of occurrences. In addition to the physiotherapist

taking note of any undesirable effect during and after the tele session or phone counselling with the project nurse, all participants are asked to report any symptoms that was not consistent with their usual physical condition presentation as a result of exercise sessions.

For a lager RCT trial to be deemed feasible, feasibility outcomes need to be attained, meaning that more than 60% of eligible patients will participate and at least 52% of the intervention group will receive more than 60% of the intended interventions.⁸⁷

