9.1 Statistical methods

Data analysis will be limited to descriptive summary statistics of the proposed endpoints, and calculation of feasibility measures, enrollment rates and dropout rates within a period. The feasibility analysis will be based on the components of process, resources, management, and scientific approach.⁵⁸ Process: number of eligible patients for enrollment; Successful recruitment rate, rate of adherence to the interventions at each time point; Rate of loss to follow up; Rates of completed questionnaires; Understanding of the questionnaires. Resources: Time to screen and consent patients, Time to conduct baseline and follow-ups; Identification of any challenges related to randomization or data collection; Identification of potential barriers of the preoperative programme. Management: Identification of any challenges related to randomization or data collection; Identification of potential barriers for the intervention. Scientific approach: Estimates of improvement in patient-reported outcomes compared to usual care, patients' response to topics and content in the programme and identification of potentially patient safety issues. As recommended for the analysis of pilot studies⁵⁸ descriptive statistics will be presented as mean and standard deviations (SD) for continuous variables and frequencies and percentages for categorial variables at baseline and follow-ups. Collected data on patient characteristics will be presented in tables. Continuous variables will be displayed as mean (SD), while categorical variables will be presented as number (n) and percentage (%). Descriptive statistics will be used to answer the primary study parameter of feasibility. Feasibility will be presented in tables and based on participation rate (n, %), reasons for nonparticipation (n, %, text), adherence to the prehabilitation program (%), dropout rates (%), reasons for dropout (n, %, text), adverse events (n, %, text). The secondary aim is to evaluate the patients' responses over time in terms of physical activity, muscle strength, functional capacity, body composition, quality of life and symptoms of depression, and anxiety. A repeated measurements analysis will be used to analyze changes over time in continuous variables. *P*- values <0.05 will be considered statistically significant.

10. Ethics

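### The rule that decides whether a larger RCT is feasible uses bare percentages, and no interval is planned; the adherence part rests on about 25 patients and is uncertain by roughly 20 percentage points either way

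*Protocol*

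**What the plan says.** Section 7.1 closes with a two-part rule for judging a larger RCT feasible: "more than 60% of eligible patients will participate", and "at least 52% of the intervention group will receive more than 60% of the intended interventions". Both parts are stated as plain percentages.

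Earlier in 7.1, under adherence, there are other thresholds. One is an uptake of at least 30% of eligible patients. The other is wide acceptance of the interventions, "with at least 70% of included participants completing 70% or more of the planned sessions in the intervention group". The section does not say how these relate to the closing rule.

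Section 9.1 sets the analysis: "Data analysis will be limited to descriptive summary statistics of the proposed endpoints, and calculation of feasibility measures". It then describes the output: "Feasibility will be presented in tables and based on participation rate (n, %), reasons for nonparticipation (n, %, text"), followed by adherence and dropout as percentages and adverse events as n, % and text. No interval is mentioned for any of them.

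On size, section 3.6 says that "there is no formal requirement for a formal power calculation", refers to general recommendations of 24 to 50 patients for pilot studies, and continues: "A sample size of 25 patients in each group was chosen". It gives no precision for the proportions that decide feasibility.

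**The concern.** The verdict on the larger RCT is the main product of this study. Under the rule it turns on whether an observed percentage falls on one side of a line. In an arm of 25, one patient is 4 percentage points, so 13 adherent patients (52%) meet the adherence condition and 12 (48%) do not. Nothing in the protocol tells the reader how far either figure could be from the true share.

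If this stays unstated, a result just above or just below a threshold will be taken as more settled than 25 patients can make it. Leaving out a power calculation is acceptable in a feasibility study. What is missing is a statement of precision for the quantities that decide.

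**Working it through.** **Inputs from the protocol.** 25 patients per group (3.6) and 1:1 allocation (3.1), so 50 in total. Adherence threshold: at least 52% of the intervention group. Uptake threshold: more than 60% of eligible patients (both 7.1).

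**Assumptions.** Two-sided 95% exact (Clopper-Pearson) intervals; independent patients; all 25 intervention patients evaluable unless stated; a number of eligible patients, which the protocol does not give. The protocol derives neither the 25 nor the 52%, so there is no calculation of its own to reproduce.

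**Adherence, smallest passing result.** 0.52 × 25 = 13 exactly. The exact limits for r of n are the 2.5% quantile of Beta(r, n − r + 1) and the 97.5% quantile of Beta(r + 1, n − r). For 13/25 these are Beta(13, 13) and Beta(14, 12), giving **31.3% to 72.2%**. The Wilson interval is 33.5% to 70.0%. As a rough check, 1.96 × √(0.52 × 0.48 / 25) = 1.96 × 0.0999 = 0.196, or about ±20 percentage points.

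Dropout changes little: 13/24 gives 32.8% to 74.5%, 12/23 gives 30.6% to 73.2% and 11/20 gives 31.5% to 76.9%.

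**How often the adherence condition alone is met.** P(X ≥ 13) for X ~ Binomial(25, p):

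| True share p | Condition met |
|---|---|
| 31% | 2.3% |
| 40% | 15.4% |
| 45% | 30.6% |
| 50% | 50.0% |
| 60% | 84.6% |
| 70% | 98.3% |

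A true 60% therefore misses the condition (100 − 84.6 = 15.4%) as often as a true 40% meets it.

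**Uptake, smallest passing result.** 50 / 0.60 = 83.3, so if 50 enrol, 83 is the largest eligible pool that still passes: 50/83 = 60.2%, whereas 50/84 = 59.5% fails. The exact interval for 50/83 is **48.9% to 70.8%**. If fewer enrol, the smallest passing results are 45/74 = 60.8% (48.8% to 72.0%) and 40/66 = 60.6% (47.8% to 72.4%). The uncertainty is about ±11 to 12 points, clearly less than for adherence.

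**If the 70%/70% criterion decides instead.** 0.70 × 25 = 17.5, so 18 patients are needed: 18/25 = 72%, exact interval 50.6% to 87.9%. If the true share on that criterion is 40%, 18 or more occurs 0.1% of the time. The pass rates in the table therefore depend on which rule applies, while the interval stays wide under either.

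**The case against.** - **An interval is a detail for a SAP, and none is shown here.** This is partly right: a SAP could add intervals. But the protocol is not merely silent. It limits the analysis to descriptive statistics, lists the outputs as n, % and text, and states the decision rule as bare thresholds. What those percentages can support belongs beside the rule.
- **Thresholds on point estimates are common in feasibility studies.** This stands. It is a weakness in precision, not a numerical error, and the thresholds can remain on the estimate.
- **Headlining 31%.** A reader might infer that a pass at 52% could easily hide a true share near 31%. That is the edge of the interval, and a true 31% would pass only 2.3% of the time. True shares of 40% to 45%, which pass 15% to 31% of the time, are the fairer picture.
- **Treating one condition as the verdict.** A reader might take 15% as the chance of wrongly declaring the RCT feasible when true adherence is 40%. The rule also requires uptake above 60%, so an overall favourable verdict is no more likely than passing the adherence condition alone. If the 70%/70% criterion also binds, it is rarer still.
- **Safety.** A reader might infer that zero events would be declared safe. The protocol does not say so: the rule has no safety threshold, and 7.1 judges safety on both the number and the nature of events. An interval is still useful there, since 0/25 has an exact upper limit of 13.7%.
- **Requiring the interval to clear the threshold.** This is a tempting remedy, but it does not work at this size. Clearing 52% would need 19 or more of 25 (lower limit 54.9%), and only 7 or fewer would fall clearly below (upper limit 49.4%). Adherence would then be undecided 93% of the time at a true 60% and 66% of the time at a true 70%.

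**Conclusion.** The point holds as a limitation on what the feasibility verdict can show. The protocol turns point percentages into that verdict and plans no statement of their uncertainty. On adherence, the smallest passing result has an exact 95% interval of 31% to 72%, and that condition alone is met 15%, 31% and 85% of the time at true shares of 40%, 45% and 60%. On uptake, the smallest passing result has an interval of about 49% to 71%, assuming 50 enrol from 83 eligible.

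The adherence figures assume 25 evaluable patients and that the 52%/60% rule decides, which section 7.1 leaves open. They describe one condition, not the overall verdict. The documents do not support a claim that the rule is arithmetically wrong or that the sample is unacceptable for a feasibility study.

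**What to change.** - **Section 9.1:** report the uptake, adherence, retention and adverse-event proportions with exact 95% confidence intervals.
- **Section 3.6:** state the precision that 25 per group gives, about ±20 percentage points on adherence.
- **Section 7.1:** state that the thresholds apply to the point estimate and that the verdict is reported together with its interval. Do not require the interval to exclude the threshold.
- **Section 7.1:** say which thresholds decide, 60% or 30% for uptake and 52%/60% or 70%/70% for adherence, and what role the others have.

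The cost is wording in three sections, with no added patients or data. The downside is that a result just above a threshold will be described less favourably.

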7.2 Secondary outcome

Secondary outcomes shown in **Table 1**. will assess the patients' responses to the multimodal prehabilitation programme and data will be collected on the following explorative outcomes shown in **Table 2**, measured at baseline, the day before surgery and 30 days after discharge.

Table 1. The patient related tests and outcome measures

Outcome variable	Measurement Instrument	What is the argument for this test or instrument?
TESTS		
Exercise capacity	6MWT	(6MWT) measures total walking distance completed in six minutes. ⁸⁸ Functional exercise capacity assessed as change from baseline by using the (6MWT) according to the American Thoracic Society guidelines. ⁸⁸
Muscle strength	30 seconds sit-to stand	Strength and endurance in leg assessed as change from baseline by 30 sec sit-to stand test. ⁸⁹
Muscle strength	Hand grip strength	The Hand grip strength measures the upper-body physical function assessed by hand grip strength using a hand-held dynamometer. ⁹⁰ Frailty assessed from baseline by Hand grip strength.
Body composition	BIA	Bio-electrical Impedance Analysis (BIA) estimates values for each body percentage, fat mass, fat-free mass, muscle mass and bone mass and total body water are assessed measuring bioelectrical impedance in the body using a Bioelectrical Impedance Analyzer. ⁹¹
Nutritional status	NRS 2002 + BMI, weight, height	Nutritional Risk Screening 2002 (NRS 2002) screening tool is a validated tool attributes scores of different levels of nutritional status to patients based on weight loss, BMI, and food intake, considering disease severity (degree of stress metabolism) and age. It is a toll recommended for detection of undernutrition and the risk of its development in hospital settings. Nutritional status assessed as changed from baseline. ⁷⁸ Body mass index BMI ⁹² at baseline,
Daily physical activity score	SENS® motion accelerometer	The SENS motion® system consist of a single-use miniature, waterproof tri-axial accelerometer, and a dedicated smart phone application. The accelerator will be placed on the lateral side of the patient's thigh at the assessment initial with a small waterproof Band-Aid. The participants will be asked to wear the SENS-accelerometer continuously for minimum four weeks during the intervention period and again post-surgery until end of follow up 30 days post index surgery. Physical activity assessed as changed from baseline by accelerator SENS innovation device. ⁷⁵
QUESTIONNAIRES		
Physical activity	Copenhagen City Heart study	Self- reported physical activity assessed from baseline by question from Copenhagen City Heart study. ⁹³ A question: "How physically active are you now?" from the Copenhagen City Heart study will be used to grade the participants physical activity in four levels (level 1-4 , i.e., 1= almost entirely sedentary, 2= light physical activity (PA) for 2-4 h per week, 3= light PA>4 h per week or more vigorous PA for 2-4 h per week, 4= more vigorous PA >4 h per week or regular heavy exercise or competitive sports several times per week.
HRQOL	SF-12	The SF-12 is a 12-item version of the SF-36 and is a brief, reliable measure of overall health status that generates both a physical and a mental component score. The questionnaire measures eight domains of health: physical function (PF), role-physical (RP), bodily pain (BP), general health (GH), vitality (VT), social functioning (SF), role-emotional (RE) and mental health (MH). Scores are calculated for each domain and aggregated into the mental component score (MCS) and the physical component score (PCS). The SF-12 is a suitable questionnaire in studies with large sample sizes having severe constraints on questionnaire length and in studies focusing on patient-based assessment of physical and mental health. ⁹⁴ Health-related quality of life (HRQL) assessed as changed from baseline by Short Form 12 (SF-12). ⁹⁴

Heart-specific QoL	HeartQoL	The HeartQoL questionnaire measures health-related quality of life in patients with ischemic heart disease, specifically angina, myocardial infarction, or ischemic heart failure. The questionnaire consists of 14 items and provides two subscales; a 10-item physical subscale and a 4-item emotional subscale which are scored from 0 (poor The HeartQoL questionnaire measures health-related quality of life) to 3 (The HeartQoL questionnaire measures health-related quality of life better). A global score is available if needed. Asks patients to remember how their heart condition has bothered them in the past four weeks. The HeartQoL questionnaire measures health-related quality of life allows clinicians and researchers to (a) assess baseline The HeartQoL questionnaire measures health-related quality of life, (b) make between-diagnosis comparisons of The HeartQoL questionnaire measures health-related quality of life and (c) evaluate changes in The HeartQoL questionnaire measures health-related quality of life in patients undergoing interventions to improve patient HRQL. ⁹⁵
Anxiety	State-Trait Anxiety Inventory	The State-Trait Anxiety Inventory (STAI) is a widely used psychological tool designed to measure two distinct types of anxiety. STAI consists of 40 items and is divided into two sections, each containing 20 items. The State-Trait Anxiety Inventory (STAI) is a widely used psychological assessment tool designed to measure two types of anxiety in adults: state anxiety (S-Anxiety) and trait anxiety (T-Anxiety). State Anxiety (S-Anxiety) reflects a temporary emotional state or condition characterized by subjective feelings of tension, apprehension, and nervousness. This type of anxiety fluctuates and is typically influenced by situational factors. The STAI measures how anxious an individual feels "right now, at this moment." Trait Anxiety (T-Anxiety) refers to a stable personality characteristic, indicating a general tendency to perceive situations as threatening and respond with anxiety across time and circumstances. It reflects a person's baseline level of anxiety in daily life. The STAI consists of 40 self-report items: 20 items assess state anxiety (e.g., "I feel calm," "I feel nervous"), and 20 items assess trait anxiety (e.g., "I am a worrier"). Respondents rate their agreement with each statement on a 4-point Likert scale. ⁹⁶
Depression	PHQ-4	Patient Health Questionnaire for depression and Anxiety (PHQ-4) includes four questions, scored on a 4-point Likert scale ranging from 0 ("not at all") to 3 "nearly every day). The questions are: 1. Depression (2 items from PHQ-9): Little interest or pleasure in doing things. Feeling down, depressed, or hopeless. Anxiety: (2 items from GAD7): Feeling nervous, anxious, or on edge. Not being able to stop or control worrying. Scoring: Each question is scored from 0-3, leading to a total score range of 0-12. The total score helps to classify the overall level of psychological distress: 0-2: Minimal or none, 3-5: mild, 6-8: Moderate, 9-12: Severe. ⁹⁷
Sense of coherence	SOC-13	The SOC-13 (Sense of Coherence-13) is a brief version of the Sense of Coherence scale developed by Aaron Antonovsky to assess an individual's ability to manage stress and maintain health. It measures three core dimensions: 1. Comprehensibility: The extent to which life is perceived as structured and understandable. 2. Manageability: The belief that one has the resources to cope with life's demands. 3. Meaningfulness: The degree to which life is seen as meaningful and worth engaging in. The SOC-13 contains 13 items scored on a 7-point Likert scale, with higher scores indicating a stronger sense of coherence and better stress resilience. ⁹⁸

Self-efficacy/self-management	PAM₁₃	The PAM ₁₃ (patient activation measure) is a 13-item survey, assesses an individual's knowledge, skill, and confidence for self-management. It categorizes patients into four levels based on their activation score, which ranges from a lack of understanding of the need for active participation in health (level one) to challenges in maintaining positive health behaviors over time (level four). The questionnaire consists of 13 questions, where each question is a statement. Respondents indicate on a scale from 1-4 how much they agree with the given statement (1 = strongly disagree, 2 = disagree, 3 = agree, 4 = strongly agree). All scores are then summed and divided by the number of answered questions, resulting in a score between 13-52. The score is then placed into one of four activity levels below, where level 1 is the lowest. ⁹⁹
Smoking status	Self-reported	Smoking status assessed as change from baseline. The number of participants successfully quitting smoking out of all active smokers
Alcohol intake status	Self-reported	Alcohol intake status assessed as change from baseline. The number of participants successfully quitting alcohol consumption out of all participants consuming alcohol.
Patient characteristics	Self-reported	Age, gender, educational level, employment, civil status
CR status	Self-reported	Last follow up (30 days post index surgery) questionnaire ask about status for: Participating in CR
Other outcomes DATA		
Adverse Events	Patient record	Measuring outcomes related to adverse events for ensuring patient safety
Complications PO	Patient record	Complications such as pneumonia, atelectasis, hemorrhage, cardiac arrhythmias, delirium
ICU-LOS/LOS	Patient record	Indicator of how well patients are recovering post-surgery and may indicate complications.
DAOH ₃₀	Patient record	DAOH ₃₀ . ^{100,101} Days alive and out of hospital is a composite measure that can be calculated based on available variables and proposed as a reliable surgical endpoint. DAOH integrates several clinical outcomes, including death and hospital readmission.
Biomarkers	Patient record	Hgb, albumin, kreatinin, CRP planned as standard blood work at baseline and post intervention.

Abbreviations: BMI: Body Mass Index; BIA: bio electrical Impedance Analysis, CR: cardiac rehabilitation; DAOH₃₀: Days alive out of hospital₃₀; HRQoL: Health related quality of life; ICU: Intensive care unit; ICU-LOS: intensive care unit – length of stay; LOS: length of stay; NRS 2002: Nutritional Risk Screening 2002; PO: post operative; PAM₁₃: Patient activation measure; PHQ-4: Patient Health Questionnaire for depression and anxiety; SF-12: Short form survey.
		

8. Data collection

Clinical and sociodemographic data as well as patient-reported outcome measurements will be collected for both groups at baseline, the day before surgery, and 30 days post-surgery as shown in **Table 2**.

TABLE 2 Schedule of enrollment, intervention, and assessment

Timepoint	Enrollement Allocation Eligibility	Baseline assessment	Min 2 weeks Homebased Prehabilitation	The day before surgery	Surgery	4 days PO	30 days post index surgery
	T ₋₁	T ₀	T ₁	T ₂	T ₃	T ₄	
Eligibility screening	X						
Informed consent, enrollment		X					
Medical history ¹ , social demographics ²		X					
Intervention + Usual care			X				
Primary Outcome							
Feasibility		X		X			X
Secondary Outcomes							
6MWT (functional capacity)		X		X			X*
BIA + NRS-2002 (baseline only)		X		X			
Hand grip strength		X		X			
Sit to stand (fysisk fridly)		X		X			X*
SENSE® Daily activity score		X		X		X	X
Copenhagen City Heart study		X					
SF-12 (HRQoL)		X		X			X
HeartQoL (Heart-specific QoL)		X		X			X
STATE-Anxiety + Trait-anxiety (baseline only)		X		X			X
PHQ -4		X		X			X
SOC-13		X					
PAM ₁₃		X		X			X
Tobacco uses status		X		X			X
Alcohol use status		X		X			X
Adverse events			X				
Other Outcomes							
PO complications ³							X
ICU -LOS /LOS							X
DAOH ₃₀							X
Participating in CR							X
Hgb, Albumin, CRP, creatinine		X				X	

¹ Euroscore II, LVEF, NYHA class, BMI, height

² Age, gender, marital status, occupational status, educational level,

³ AF, re-operation, pneumonia, delirium, deep sternal infection, stroke. *Test foretages enten på Rigshospitalet eller lokalt på hjemsygehus.

Abbreviations: DAOH₃₀: Days alive and out of hospital; CR: Cardiac rehabilitation; PO: postoperative; AF: Atrial fibrillation; ICU-LOS: intensive care unit length of stay; LOS: length of stay; NRS-2002: Nutrition Risk Screening; PAM₁₃: Patient activation measures; PHQ-4: Patient Health Questionnaire; SOC-13: Sense of Coherence-13.

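### The outcome labelled Depression in Table 1 is given only the PHQ-4 total, half of which is anxiety items, so its level or change cannot be attributed to depression

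*Protocol*

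**What the plan says.** Protocol section 7.2, Table 1, lists an outcome variable called Depression with the PHQ-4 as its instrument. No other row is assigned to depression. The description reads:

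- Instrument: "Patient Health Questionnaire for depression and Anxiety (PHQ-4) includes four questions".
- Depression half: "Depression (2 items from PHQ-9): Little interest or pleasure in doing things", followed by a second depression item.
- Anxiety half: "Anxiety: (2 items from GAD7): Feeling nervous, anxious, or on edge", followed by a second anxiety item.
- Score: "Each question is scored from 0-3, leading to a total score range of 0-12".
- Meaning of the score: "The total score helps to classify the overall level of psychological distress", with the bands "0-2: Minimal or none, 3-5: mild, 6-8: Moderate, 9-12: Severe".

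The row describes no depression subscore. Anxiety has its own Table 1 row, with the STAI. Table 2 schedules the PHQ-4 at baseline, the day before surgery and 30 days after surgery.

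Section 9.1 includes "quality of life and symptoms of depression, and anxiety" among the patient responses to be evaluated over time. It adds: "A repeated measurements analysis will be used to analyze changes over time in continuous variables", with P < 0.05 as the significance threshold. Section 2.2 says that outcome levels, variation and changes are collected because they can inform the sample size of the future RCT.

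**The concern.** The row names one construct and scores another. Its label is Depression, but the score it describes is, in its own words, a measure of overall distress built equally from depression and anxiety items. Elsewhere the protocol keeps the two apart: anxiety has its own row and instrument, section 9.1 names both symptoms, and section 10.3 expects the programme to reduce both.

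Three things are at stake.

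- **Attribution.** Section 1.2.1 describes waiting for surgery as a time of heightened anxiety, and the counselling in section 6.2.3 targets stress, anxiety and depression. The anxiety items could move on their own, in either direction. A fall in the total might then be read as a benefit on depression, or a rise before surgery might hide one.
- **Overlap.** Anxiety would enter both the anxiety result (STAI) and the result labelled depression.
- **Planning.** A standard deviation or change taken from a 0 to 12 distress total is not that of a 0 to 6 depression score, so it is the wrong input for a future trial that specifies depression.

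**Working it through.** **Inputs, all from the PHQ-4 row of Table 1.** Four items, each 0 to 3; two depression items (d1, d2) and two anxiety items (a1, a2); bands 0–2, 3–5, 6–8 and 9–12.

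**1. The plan's own figure.** Minimum 4 × 0 = 0; maximum 4 × 3 = 12. The stated range of 0 to 12 is reproduced.

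**2. Share of anxiety in the total.** Maximum from the anxiety items is 2 × 3 = 6, and 6/12 = 50%.

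**3. A patient with no depressive symptoms.** Set d1 = d2 = 0, so that total = a1 + a2. Of the 4 × 4 = 16 possible anxiety answer pairs:

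| Total | Answer pairs | Band |
|---|---|---|
| 0 | 1 | Minimal or none |
| 1 | 2 | Minimal or none |
| 2 | 3 | Minimal or none |
| 3 | 4 | Mild |
| 4 | 3 | Mild |
| 5 | 2 | Mild |
| 6 | 1 | Moderate |

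Ten of the 16 (4 + 3 + 2 + 1) fall in Mild or higher. This counts answer patterns. It is not an estimate of how many patients would be affected.

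**4. What a given total says about depression.** Depression subscore = total − (a1 + a2), where a1 + a2 runs from 0 to 6.

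- Total 3: the subscore can be 0 to 3.
- Total 6: the subscore can be 0 to 6, its entire range.
- Total 9: the subscore can be 3 to 6. The Severe band therefore needs at least 9 − 6 = 3 depression points.

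In the other direction, with a1 = a2 = 0 and both depression items at 3, the total is also 6. The total cannot tell that patient from one with maximal anxiety items and no depressive symptoms.

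**5. Consequence for planning (illustration under assumptions that are not in the protocol).** Suppose the two subscores have equal standard deviation s and correlation r, and an effect δ acts on the depression items only.

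- SD of total = s × √(2 + 2r)
- Standardised effect on the total ÷ standardised effect on the depression subscore = [δ / (s√(2 + 2r))] ÷ [δ / s] = 1/√(2 + 2r)

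| r | SD of total ÷ SD of subscore | Ratio of standardised effects |
|---|---|---|
| 0.3 | √2.6 = 1.61 | 0.62 |
| 0.5 | √3.0 = 1.73 | 0.58 |
| 0.7 | √3.4 = 1.84 | 0.54 |

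Over this range the two scores differ in SD by a factor of about 1.6 to 1.8, so one cannot stand in for the other in a sample-size calculation.

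**The case against.** The strongest reply is that the row hides nothing. It gives the instrument's full name, lists the depression and anxiety items separately and calls the total a measure of distress; Table 2 lists the instrument simply as PHQ-4. The scoring text stands in a column that explains why each instrument was chosen, and no sentence says outright that the total will be analysed as the depression endpoint. Deriving subscores is commonly left to a statistical analysis plan, which is not at hand. The worked example is one extreme response pattern, no feasibility criterion uses the PHQ-4, and the subscores can be derived at any time from items already collected.

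Much of this stands, and it limits the weight of the point. It does not remove the mismatch. Table 1 does describe scores for other instruments: it names the two SF-12 component scores and the two HeartQoL subscales. For the PHQ-4 it gives only a total, under a label that the total does not measure. A later plan could add subscores, but the protocol row would still need correcting.

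A reader might go further and infer that an anxious patient without depression is counted as depressed. The protocol does not support that. It has no depression cut-off, no case definition and no count of depressed patients; the bands are bands of distress, and moderate distress is a fair description of a patient with maximal anxiety items. A reader might also infer that a fall driven by anxiety will be reported as an effect on depression. The plan leaves that possible but does not state it.

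**Conclusion.** The point holds as a mismatch between an outcome label and the only score described for it. Half of the 0 to 12 total comes from anxiety items, and a mid-range total of 6 carries no information on whether the depression subscore is 0, 6 or anything between. If the row is followed as written, the depression result named in section 9.1 would be a mixed distress score. Neither its level, its change nor its standard deviation should be described as that of depression.

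The score arithmetic rests only on the item and band definitions in Table 1. The dilution figures in step 5 rest on assumed equal SDs, correlations of 0.3 to 0.7 and an effect confined to the depression items; they illustrate the difference and do not predict this trial's data. How often real patients would show a wide gap between the total and the depression subscore cannot be determined from the protocol.

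The importance is low: one exploratory secondary outcome in a feasibility study of 25 per group, with no progression criterion attached. The correction is nonetheless worthwhile, because section 2.2 intends these outcomes to inform the next trial.

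**What to change.** In Table 1:

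1. Name the sum of the two depression items (0 to 6) as the depression outcome, and state that this is the score analysed for depression under section 9.1.
2. Report the sum of the two anxiety items (0 to 6) separately, alongside the STAI.
3. Keep the 0 to 12 total and its bands if wanted, labelled as psychological distress.

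When estimates are passed to the future RCT, give the mean, SD and change for each score under its own name.

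The cost is one table edit and two derived variables. All four items are already scheduled at the three time points, so there are no new data, no added patient burden and no change to the sample size.
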